9.3. Interim Analyses and Data Monitoring Committee

9.3.1. Interim Analyses

There is no interim analysis in this study.

9.3.2. Data Monitoring Committee

An independent DMC will review safety and efficacy data from this study for their recommendation. Ad hoc meetings will be convened, as appropriate. The role and scope of the DMC will be further described in a separate charter.

9.4. Multiple Comparisons/Multiplicity

No adjustment on type I error will be performed in this study.

9.5. Subgroup Analyses of Efficacy

No subgroup analysis of efficacy is planned in this study.

10. SAFETY ANALYSES

Safety analyses will be performed using the LTSE population. No inferential comparison of safety endpoints will be performed, unless otherwise specified.

10.1. Exposure to Study Treatment

The extent of exposure will be summarized using descriptive statistics.

Duration of exposure (days) to investigational product will be calculated as follows:

- Exposure to investigational product = [(Date of last investigational product dose – Date of 1st investigational product dose) + 1] – Total duration of temporary investigational product discontinuation

The duration of each incidence of temporary investigational product discontinuation will be calculated as follows:

- Duration of temporary discontinuation of investigational product = (Date of restart of investigational product – Date of temporary discontinuation of investigational product) + 1.

The total duration of temporary investigational product discontinuation is the sum duration of temporary discontinuation of investigational product over each incidence of discontinuation.

Total subject exposure to investigational product will be calculated by adding the doses taken by a subject during the study and will be summarized using descriptive statistics.

A summary of subjects who had an increase in dose and who had a decrease in dose at least once during the study will be provided in terms of frequency count (n) and percentages (%).

Subject's overall compliance (%) with investigational product will be calculated as follows:

- $\text{number of tablets consumed during study} / \text{number of tablets expected to be consumed during study} * 100$

where

- $\text{number of tablets consumed during study} = \text{number of tablets dispensed} - \text{number of tablets returned}$

Subject compliance with investigational product will be summarized using descriptive statistics. Percent compliance will be summarized separately for subjects who completed the study versus those who withdrew early so as to distinguish between those subjects who were compliant throughout the entirety of the study versus those who were compliant until they withdrew from the study.

All exposure data will be presented in a by subject data listing.

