8.4. Subject Withdrawal Criteria

Subjects who are discontinued from investigational product should be requested to continue with study visits until Month 60/EOS. Subjects who discontinue investigational product may be requested to come in for an Unscheduled Visit at the discretion of the Investigator depending on the timing of their next scheduled study visit.

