14.1.3.1. Severity of Pruritus (as an Adverse Event)

To ensure consistency in reporting, pruritus AEs must be graded for severity (i.e., intensity). As pruritus is a subjective symptom, clinical judgment should be used to determine its severity and management, as shown in Table 10. In order to assess the potential improvement in pruritus with treatment, baseline pruritus presence (yes/no) and severity (as shown in Table 10) will be determined.

Table 10: Severity of Pruritus

Pruritus Grade	Clinical Description of Severity for Pruritus and Medical Intervention
1=Mild	Mild or localized; topical intervention indicated
2=Moderate	Intense or widespread; intermittent; skin changes from scratching (e.g., edema, papulation, excoriations, lichenification, oozing/crusts); oral intervention indicated; limiting instrumental activities of daily living
3=Severe	Intense or widespread; constant; limiting self-care activities of daily living or sleep; oral corticosteroid or immunosuppressive therapy indicated

Since pruritus is a subjective symptom and the occurrence and magnitude of which are not readily measured by objective tools, clinical judgment needs to be applied in the management of each subject. Managing OCA-related pruritus may help improve tolerance in those subjects who experience problematic pruritus and may otherwise discontinue from the study prematurely. General guidance for the management of subjects experiencing significant pruritus includes the following:

- Drug holiday: A drug holiday is defined as an Investigator's "prescribed" complete interruption of dosing for 1 or more consecutive days (i.e., nondaily dosing does not constitute a drug holiday). Details of drug holidays and/or nondaily dosing regimens should be recorded in the eCRF. If the drug holiday lasts more than 30 days, the subject should be permanently discontinued from investigational product but requested to continue with study visits until Month 60/EOS.
- Per [Section 8.4.1.1](#), subjects with pruritus \geq Grade 3 in severity and possibly, probably, or definitely related to the investigational product must discontinue investigational product but are encouraged to continue study visits.

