- Subjects taking BAS (including cholestyramine and its derivatives, colestipol, colesevelam, or other BAS) or aluminum hydroxide- or smectite-containing antacids should refrain from using these drugs for the management of pruritus during the trial. The use of BAS may alter the interpretation of the effects of BZF on pruritus.
- Other therapies may be tried as deemed clinically appropriate.
- Rifampin should be used with caution in patients with PBC due to the hepatotoxicity concerns as specified in the rifampin USPI.
- Less frequent dosing of investigational product (e.g., on alternate days) may be administered, after which, subjects may return to their original daily dose as soon as tolerated.

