3.4. Sample Size Determination

The sample size in this study is not calculated based on statistical consideration.

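### SAP 10.1 counts each dosing interruption 1 or 2 days too long, and its compliance split puts subjects who stopped product early among the completers

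*SAP*

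**What the plan says.** SAP 10.1 (Exposure to Study Treatment) defines duration of exposure as the inclusive count from first to last dose, less the time off drug: "Date of last investigational product dose – Date of 1st investigational product dose) + 1] – Total duration of temporary investigational product discontinuation". Each interruption is measured as "Date of restart of investigational product – Date of temporary discontinuation of investigational product) + 1", and the interruptions are summed. The section does not say whether the discontinuation date is the last day dosed or the first day missed.

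It also plans "A summary of subjects who had an increase in dose and who had a decrease in dose at least once during the study", without defining dose. Compliance is tablets consumed (dispensed minus returned) over tablets expected, and expected is not defined. "Percent compliance will be summarized separately for subjects who completed the study versus those who withdrew early"; the reason given is to tell subjects who complied for the whole study from those who complied only until they left.

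The protocol supplies one strength, one tablet once daily, swallowed whole (9.1.1). For pruritus it allows drug holidays of one or more consecutive days. It also says "Less frequent dosing of investigational product (e.g., on alternate days) may be administered", while "nondaily dosing does not constitute a drug holiday" (14.1.3.1). Section 8.4 states: "Subjects who are discontinued from investigational product should be requested to continue with study visits until Month 60/EOS". Sections 7.6 and 8.4.2 ask the same.

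**The concern.** An inclusive count, with its + 1, is right when both end dates belong to the interval. First dose to last dose is such an interval. An interruption that ends on the restart date is not, because the subject takes a tablet that day. The restart day is counted once as exposure and then removed as time off drug. The + 1 matches the general day-count rule in SAP 5.4, which may be where it came from.

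The compliance split has a different fault. Completing the study and completing treatment are separate events under this protocol, because subjects who stop product are asked to keep attending. A table split by study completion therefore cannot isolate those who took drug throughout.

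At stake is the accuracy of two descriptive tables in a single-arm study whose primary objective is long-term safety and tolerability.

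**Working it through.** There is no planned figure to reproduce: the study tests no hypothesis, and SAP 3.4 says "The sample size in this study is not calculated based on statistical consideration". The check applies the SAP 10.1 formulas to simple dosing records. The records are illustrative assumptions; the formulas are the SAP's.

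**Interruption length.** Let r be the restart date, d the first missed day and l the last dosed day, so d = l + 1.

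- True days off = r − d = r − l − 1.
- SAP, if the discontinuation date is d: r − d + 1, which is 1 day too long.
- SAP, if the discontinuation date is l: r − l + 1, which is 2 days too long.

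Example: dosed Days 1–10, off Days 11–17, dosed Days 18–20. Days dosed = 10 + 3 = 13.

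- Discontinuation date Day 11: 20 − (18 − 11 + 1) = 12 days of exposure.
- Discontinuation date Day 10: 20 − (18 − 10 + 1) = 11 days of exposure.

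The SAP's other exposure measure, the sum of doses taken, gives 13 for the same subject.

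The excess is constant, so it matters most for short gaps:

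| True days off | SAP, date = first missed day | SAP, date = last dosed day |
|---|---|---|
| 1 | 2 | 3 |
| 7 | 8 | 9 |
| 30 | 31 | 32 |

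It also accumulates. In a 365-day record of daily dosing with one-day holidays:

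| One-day holidays | True dosing days | SAP (first missed day) | SAP (last dosed day) |
|---|---|---|---|
| 6 | 365 − 6 = 359 | 365 − 12 = 353 | 365 − 18 = 347 |
| 12 | 365 − 12 = 353 | 365 − 24 = 341 | 365 − 36 = 329 |

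Over 60 months, 60 × 365.25/12 ≈ 1826 days (the SAP 5.4 month), a single gap shifts exposure by 1/1826 to 2/1826, or about 0.05% to 0.11%.

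**Compliance.** Take a subject who swallows every tablet, stops product and attends to Month 60. The subject has completed the study and joins the completer group.

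| Product stopped | Days on product | Expected to last dose | Expected to Month 60 |
|---|---|---|---|
| Month 3 | 91 | 100% | 91/1826 = 5.0% |
| Month 12 | 365 | 100% | 365/1826 = 20.0% |
| Month 36 | 1096 | 100% | 1096/1826 = 60.0% |

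Neither denominator yields a value that belongs in a group meant to show adherence over the whole study.

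**Reduced frequency.** Alternate-day dosing for 180 days is 90 tablets. It is not a drug holiday, so nothing is subtracted and duration of exposure is 180 days. Compliance within the spell is 90/180 = 50% if expected means daily, or 100% if it means as prescribed. Over a 365-day record containing that spell, the daily reading gives (185 + 90)/365 = 75.3%.

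**The case against.** The strongest reply is that little turns on this. One gap moves exposure by 1 or 2 days, and the documents do not say how often short holidays occur. The SAP plans crude incidences and no exposure-adjusted rates, so the day error reaches no safety rate. Product discontinuation is tabulated in SAP 6 with separate end-of-treatment disposition, and SAP 10.2.3 summarises adverse events leading to product withdrawal. All of that stands, and it limits the size of the point. It does not make the formula right or let the compliance split serve its stated purpose.

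Three stronger readings are tempting, and the documents do not support them.

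- **A reader might infer that the dose-change table must be empty, so that almost no dose modification would be reported.** That follows only if dose means the amount per administration, which the SAP does not say. Protocol 7.6 treats frequency changes under its heading on dosage adjustment, and 14.1.3.1 describes subjects on alternate days as later going back to the daily dose they had. A frequency cut can therefore be read as a decrease. The sum of doses taken would also show it, and exposure data are listed by subject. The gap is an undefined term.
- **A reader might blame the single tablet strength for both errors.** The + 1 and the completer split would be wrong for any regimen. For alternate-day dosing the duration runs the other way: off-days are not subtracted, so it overstates days dosed.
- **A reader might say that a 30-day holiday, computed as 31 or 32 days, breaches the protocol's 30-day limit.** That limit is site guidance on pruritus holidays, and no SAP rule applies the computed gap to it. Interruptions for laboratory criteria (Protocol Table 4) are governed by a separate restart rule with its own 30-day minimum.

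**Conclusion.** Two errors stand in SAP 10.1 as written. First, each interruption is overcounted by exactly 1 or 2 days, depending on which date is recorded as the discontinuation, and duration of exposure is understated by the same amount. The formula would be correct only if restart meant the last day off drug, which the wording does not support. The effect is small for most subjects and becomes visible only with many short gaps.

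Second, the compliance split by study completion groups subjects who stopped product and stayed to Month 60 with those treated throughout, contrary to its stated purpose. This is confined to that table and does not affect subjects who stopped product and also left the study. The 20% and 100% figures assume full compliance until stopping at Month 12; the spread arises because expected tablets are undefined.

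The meaning of a decrease in dose needs clarifying, but it is not a demonstrated omission.

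**What to change.** In SAP 10.1:

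1. Define the discontinuation date as the first day without drug, and compute each interruption as restart date − discontinuation date, with no + 1. If the eCRF holds the last dosed day instead, use restart − last dosed day − 1.
2. Split compliance by completed versus discontinued investigational product.
3. Define expected tablets as those prescribed from first to last dose, following the regimen and holidays recorded in the eCRF.
4. As a clarification, state that a decrease in dose includes a reduction in prescribed frequency, and note that duration of exposure does not subtract the off-days of nondaily dosing.

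The cost is SAP wording and table programming. Protocol 14.1.3.1 already has drug holidays and nondaily regimens recorded in the eCRF, and no dosing rule is touched.

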The adjudication of potential events will be based on available source documentation, including but not limited to individual clinical study data, hospital records, discharge summaries, and/or death certificates. The adjudication committees will not receive any individual subject treatment or site-specific information. All protected health information will remain confidential and will not be available to the adjudication committee. The assessment of events will be conducted in compliance with study-specific procedures, manuals, Good Clinical Practice (GCP), and all other applicable regulatory requirements, including the archiving of essential documents.

Investigational Products, Dosage, and Mode of Administration:

The single FDC tablet must be swallowed whole and not be chewed, divided, or crushed and must be taken with food and water (ad libitum) throughout the study period. Subjects are requested to take medication in the morning. Specific instructions for dosing will be provided for PK assessment days.

- FDC tablet (OCA 5 mg + BZF 400 mg SR), once daily

The FDC tablet will be dispensed in a bottle. Each subject should take 1 tablet daily. The FDC tablet will be provided for use only in this study and is not to be used for any other purpose. The Principal Investigator or designee will maintain a full record of investigational product accountability, including records of individual subject dispensing and final return or disposition (as directed by the Sponsor).

Duration of Treatment:

The total duration of Study 977-311 per subject will be a maximum of 60 months from day of study entry. The end of study is defined as the date of the last visit of the last subject.

Statistical Methods:**Analysis Populations:**

LTSE Population: The LTSE Population will include all subjects who receive at least 1 dose of the FDC tablet in Study 977-311.

Pharmacokinetic Population: The PK Population will include all subjects in LTSE Population who receive the FDC tablet in Study 977-311 and have a PK sample(s) without any major protocol deviations that could potentially affect plasma exposure.

Pharmacodynamic Population: The PD Population will include all subjects with a baseline assessment and at least 1 on-treatment assessment without any major protocol deviations that could potentially affect results.

Safety Analyses:

The LTSE Population will be the primary population used for safety analyses.

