9.3. Treatment Compliance

The Investigator should assess the subject's compliance with dosing of investigational product at each study visit after Day 2.

Subjects should be instructed to retain all bottles of investigational product, even if empty, and to provide them to the Investigator at the indicated visits in [Table 3](#). The Investigator or designee should perform investigational product accountability (i.e., count of returned tablets) and, if applicable, follow up with the subject to retrieve any investigational product bottles that have not been returned.

If the Investigator has concerns about a subject's dosing compliance, he or she should discuss this with the subject, assess the reasons for noncompliance and the likelihood that the subject will remain noncompliant, and notify the Sponsor accordingly.

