10. INVESTIGATIONAL PRODUCT MATERIALS AND MANAGEMENT

10.1. Investigational Product

The FDC investigational product will be supplied as white, oval, film-coated tablets. The FDC tablet combines OCA and BZF in a single tablet. The FDC tablet formulation is a bilayer, film coated tablet containing 2 active components: OCA 5 mg IR with BZF 400 mg SR. The FDC tablets are 9 mm by 19 mm oval tablets debossed with “INT” on 1 side and “3547” on the other side. Each FDC tablet contains [REDACTED] as a

release controlling agent for the active BZF along with the following inactive ingredients:

[REDACTED] The FDC will be provided as tablets for oral administration in high density-polyethylene (HDPE) bottles with heat induction seals and child-resistant closures, containing 100 tablets. All FDC tablets will be manufactured according to Good Manufacturing Practice (GMP).

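### Tablets in bottles never recovered count as swallowed, so they can bias SAP compliance only upward, most of all in early withdrawals

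*SAP*

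**What the plan says.** SAP 10.1 (Exposure to Study Treatment) gives three separate quantities.

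- **Compliance.** A subject's "overall compliance (%) with investigational product will be calculated as follows": tablets consumed over tablets expected during the study, times 100. Consumed means dispensed minus returned. There is one figure per subject for the whole study, and it is summarised separately for completers and early withdrawals.
- **Duration.** "Duration of exposure (days) to investigational product will be calculated as follows", from first and last dose dates less temporary interruptions. It uses no tablet counts.
- **Total exposure.** "Total subject exposure to investigational product will be calculated by adding the doses taken by a subject during the study". The source of doses taken is not stated.

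Protocol 9.3 (Treatment Compliance) tells subjects to keep and bring back every bottle, including empty ones. Sites count the returned tablets and, where needed, "follow up with the subject to retrieve any investigational product bottles that have not been returned". Neither document says how to score a bottle that is never recovered.

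On supply, Protocol 10.1 describes bottles "containing 100 tablets", and the Protocol Synopsis states "Each subject should take 1 tablet daily". Protocol 10.2 allows several bottles per visit without giving the number.

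**The concern.** Under dispensed minus returned, a bottle that was lost, kept or left unopened contributes zero returns, so all its tablets are scored as swallowed. The less a subject brings back, the more compliant that subject appears. Protocol 9.3 foresees missing bottles, so this will arise in ordinary conduct of the study.

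Early withdrawals are the group most exposed. Under Protocol 8.4.2.2 a subject is lost to follow-up only after contact attempts have failed, and under 8.4.3 early-termination evaluations are done only as far as possible. The last supply dispensed to such subjects will often not be counted, and their denominators are short. The SAP splits out this group in order to show whether those who left were compliant until they left, which is where the rule is least reliable.

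A score above 100% is also ambiguous. It could mean extra tablets taken, which Protocol 14.1.5 wants assessed, or only a missing bottle.

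**Working it through.** Neither document states a compliance figure, so there is none to reproduce. The SAP 10.1 formula was applied directly.

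**Inputs**

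- 1 tablet per day (Protocol Synopsis).
- 100 tablets per bottle (Protocol 10.1).
- Visits every 6 months from Month 6 onward (Protocol 7.1.1 and Table 3).
- Month length 365.25/12 = 30.4375 days (SAP 5.4). Expected tablets are therefore 182.6 for 6 months, 213.1 for 7 months and 1826.25 for 60 months.
- Assumption: the fewest bottles that cover the interval, so 2 bottles (200 tablets) per 6 months.
- Assumption: leftover tablets from all other intervals are returned and counted.

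**Formula:** score = 100 × (dispensed − returned) / expected.

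**1. One 6-month interval.** Bottle 1 is taken, and bottle 2 is unopened and never returned.

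- Scored: 200/182.6 = 109.5%.
- True: 100/182.6 = 54.8%.

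**2. The same interval inside overall compliance**, which is the quantity the SAP reports, with perfect dosing in all other intervals. For expected total E, scored = (E − 182.6 + 200)/E and true = (E − 182.6 + 100)/E.

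| Follow-up | E | Scored | True | Gap (100/E) |
|---|---|---|---|---|
| 12 months | 365.25 | 104.8% | 77.4% | 27.4 points |
| 24 months | 730.5 | 102.4% | 88.7% | 13.7 points |
| 60 months | 1826.25 | 101.0% | 95.5% | 5.5 points |

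**3. Early withdrawal.** Dosing is perfect and earlier leftovers are returned. Contact is lost at Month 7, with the 200 tablets dispensed at Month 6 unreturned. The SAP does not define expected tablets for this case; assume they run to Month 7.

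- Scored: (182.6 + 200)/213.1 = 180%.
- True: 213.1/213.1 = 100%.
- Unreturned tablets counted as not taken: 182.6/213.1 = 85.7%.

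**4. Extreme case.** Nothing is returned in 60 months. One bottle at each of the first three dispensings plus 9 × 2 bottles gives 2100 tablets, and 2100/1826.25 = 115.0%.

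**The case against.** Dispensed minus returned is a simple pill count with a familiar limitation, and the protocol has safeguards. Subjects keep all bottles, sites retrieve missing ones and report compliance concerns (Protocol 9.3), and the study monitor reviews accountability records (Protocol 10.5). The SAP reports maximum values and lists exposure data by subject, so scores above 100% would be visible. PK samples through Month 60 (Protocol 13.1) give separate evidence of dosing. An unreturned bottle may also have been emptied and thrown away, in which case the formula is right.

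Much of this stands. The safeguards reduce the number of unrecovered bottles but give no rule for those that remain. Nor will every affected subject show a score above 100%, because missed doses elsewhere can offset the unreturned tablets. The lack of a cap is not a fault, since a cap would hide both lost bottles and possible overdosing.

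Three stronger readings are tempting, and the documents do not support them:

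- **Overall compliance of about 110% for one lost bottle.** The 109.5% is for a single interval. The SAP reports an overall figure, and at 60 months the same bottle gives 101.0%.
- **Total exposure is overstated.** Duration uses dates, and the source of doses taken is unstated. Protocol 14.1.3.1 has drug holidays and non-daily dosing recorded in the eCRF, so another source is possible. Table 3 is partly redacted, so the absence of a diary row there shows nothing.
- **Adverse event rates are distorted.** SAP 10.2 plans subject and crude incidences in the LTSE Population, which requires only one dose. Compliance enters none of them.

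**Conclusion.** The point holds for the compliance summary. Followed exactly, SAP 10.1 treats unrecovered tablets as taken, and the resulting error is either zero or upward. One full unopened bottle adds 100 tablets to the numerator. That is 5.5 points of overall compliance at 60 months, and far more when follow-up is short. In early withdrawals even a fully adherent subject can score about 180%, and a few such values would distort that group's mean.

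These sizes rest on 2 bottles per 6-month interval and, for the Month 7 case, on expected tablets running to the date of loss. How often bottles go unreturned is not given, so the effect on the study-level summary cannot be stated. The consequence is for interpretation: in a single-arm study whose primary objective is long-term safety and tolerability, adherence may look better than it was.

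**What to change.** In SAP 10.1:

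1. Class tablets in unrecovered bottles as unaccounted for.
2. Report compliance twice, with these tablets counted as taken (the current rule, an upper bound) and as not taken (a lower bound). Do this overall, for completers and for early withdrawals.
3. Report the number and percent of subjects with unreturned bottles.
4. Flag values above 100% without capping them.
5. State the data source for doses taken. If it is the tablet count, apply the same bounds to total exposure.

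Bounds are preferable to restricting the calculation to intervals with every bottle returned, because that would drop the intervals in which non-adherence may be most likely.

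The cost is SAP wording and a little programming on accountability data already collected. The report will show a range in place of a single, more favourable figure. No study procedure changes.
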